## 7.3. RETESTS, UNSCHEDULED VISITS AND EARLY TERMINATION DATA

In general, for by-visit summaries, data recorded at the nominal visit will be presented. Unscheduled measurements collected prior to the first dose of study medication will contribute to the derivation of the baseline value.

Unscheduled measurements collected post baseline will not be included in by-visit summaries but will contribute to the EOS markedly abnormal post-baseline vital signs (MAPVS), markedly abnormal post-baseline laboratory value (MAPLV) and best/ worst case value where required (e.g. shift table).

Early termination (ET) data collected post baseline will be assigned to the next planned visit for that assessment. If the next scheduled visit is more than 14 days, then the ET data will not be included in the by-visit summary tables but will be included in the MAPVS, the MAPLV and the listings. This mapping will be done for all data points used in the PK and safety analyses.

In the case of a retest (same visit number assigned), the latest available measurement for that visit will be used for by-visit summaries.

Listings will include scheduled, unscheduled, retest and early discontinuation data.

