14.3.5.2. Clinical Laboratory Assessments

All summaries involving clinical chemistry, hematology, and urinalysis tests will be based on the Safety population.

Descriptive statistics for observed value and change from baseline will be displayed at each visit by treatment for each chemistry, hematology, and urinalysis laboratory test measured on a continuous scale.

Serum prolactin values will be summarized by treatment and gender.

The normal reference ranges for laboratory tests will be used to determine whether the laboratory test value is below, within, or above the normal range. Shifts from baseline will be produced by treatment to show the percentage of subjects with laboratory test values below, within, and above the normal range.

The number and percentage of subjects with a Markedly Abnormal Post-baseline Laboratory value (MAPLV, to be defined in the SAP) for select parameters will be summarized by treatment.

The data listings for laboratory parameters will flag values outside of the reference range.

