## **18.2. LABORATORY EVALUATIONS**

Results from the central laboratory will be included in the reporting of this study for clinical chemistry, hematology, and urinalysis Lipid Panel, Thyroid Panel, Coagulation Panel Urine Drug Screening, Serology Panel, and Other Tests.

A list of laboratory assessments to be included in the outputs is included in appendix II/ the protocol, Section 21.

ISAF population will be used for all laboratory summaries. OSAF population will be used for the listings.

Presentations will use standard international (SI) Units

---

Document:

Author:

Version Number:  
Version Date:

Final Draft  
11APR2019

Template No: CS\_TP\_BS016 Revision 4  
Effective Date: 01Apr2016

Reference: CS\_WI\_BS005

Quantitative laboratory measurements reported as “< X”, i.e. below the lower limit of quantification (BLQ), or “> X”, i.e. above the upper limit of quantification (ULQ), will be converted to X for the purpose of quantitative summaries, but will be presented as recorded, i.e. as “< X” or “> X” in the listings.

Note that handling of retests and unscheduled measurements are included in Section 7.3 to save repetition in different sections of the SAP

The following summaries will be provided for laboratory data:

- Actual and change from baseline by visit (for quantitative measurements) and by treatment.
- Shift from baseline by treatment and visit of subject with laboratory values below, within, and above the normal range.
- Incidence of subjects with a Markedly Abnormal Post-Baseline Laboratory value (MAPLV) for select parameters by treatment.
- Actual and change from baseline for selected serum chemistry parameters (Hemoglobin, Haematocrit, Uric Acid and serum prolactin) values by visit, treatment and by gender.
- Shift from baseline by visit, treatment and by gender of subject for selected serum chemistry parameters (Hemoglobin, Haematocrit, Uric Acid and serum prolactin) below, within, and above the normal range.
- Incidence of subjects with a Markedly Abnormal Post-Baseline Laboratory value (MAPLV) for selected serum chemistry parameters (Hemoglobin, Haematocrit, Uric Acid and serum prolactin) values by treatment and by gender.
- Data listings for all laboratory parameters along with comments will be provided. Results outside of the reference range will be flagged.

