Table 14.3.2.2	Adverse Events Leading to Study Discontinuation - Injectable Safety Population
Table 14.3.4.1.1	Serum Chemistry: Actual Value and Change from Baseline by Scheduled Timepoint and Treatment - Injectable Safety Population
Table 14.3.4.1.2	Serum Chemistry: Shift from Baseline by Scheduled Timepoint and Treatment - Injectable Safety Population
Table 14.3.4.2.1	Hematology Parameters: Actual Value and Change from Baseline by Scheduled Timepoint and Treatment - Injectable Safety Population
Table 14.3.4.2.2	Hematology: Shift from Baseline by Scheduled Timepoint and Treatment – Injectable Safety Population
Table 14.3.4.3.1	Urinalysis: Actual Value and Change from Baseline by Scheduled Timepoint and Treatment - Injectable Safety Population
Table 14.3.4.3.2	Urinalysis: Shift from Baseline by Scheduled Timepoint and Treatment - Injectable Safety Population
Table 14.3.4.4	Summary of Markedly Abnormal Post-Baseline Laboratory Value (MAPLV) by Treatment - Injectable Safety Population
Table 14.3.5.1	Vital Signs: Actual Value and Change from Baseline by Scheduled Timepoint and Treatment - Injectable Safety Population
Table 14.3.5.2	Summary of Abnormal Post-Baseline Vital Signs (MAPVS) Values by Treatment - Injectable Safety Population
Table 14.3.5.3	Incidence of Orthostatic Hypotension and Orthostatic Tachycardia by Treatment - Injectable Safety Population
Table 14.3.5.4.1	ECG: Actual Value and Change from Baseline by Scheduled Timepoint and Treatment - Injectable Safety Population
Table 14.3.5.4.2	Summary of ECG Categories of Markedly Abnormal Criteria by Treatment - Injectable Safety Population

Document:

Author:

Version Number:  
 Version Date:

Final Draft  
 11APR2019

Template No: CS\_TP\_BS016 Revision 4  
 Effective Date: 01Apr2016

Reference: CS\_WI\_BS005

Statistical Analysis Plan

PROTOCOL D1052024  
 Page 63 of 66

Number	Title
Table 14.3.5.5.1	Summary of Columbia Suicide Severity Rating Scale (CSSRS) by Scheduled Timepoint and Overall Screening/Baseline and Last Visit Questionnaire - Injectable Safety Population
Table 14.3.5.6.1	Investigator Injection Site Reaction by Treatment and Schedule Timepoint - Injectable Safety Population
Table 14.3.5.6.2	Subject Injection Site Reaction Pain by Treatment and Schedule Timepoint - Injectable Safety Population
Figure 14.2.1.1	Mean (+SD) Lurasidone Serum Concentration-time Profiles by Dose on Linear and Semi-logarithmic Scales - Pharmacokinetic Population

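### SAP 7.3 sends unscheduled laboratory values to a worst-case shift that SAP 18.2 and the table list do not define, so some out-of-range results reach only the listings

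*SAP*

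**What the plan says.** SAP 7.3 sets the rule for data collected off schedule: "Unscheduled measurements collected post baseline will not be included in by-visit summaries". Such values still count towards the markedly abnormal vital sign and laboratory tables (MAPVS and MAPLV) and towards a "best/ worst case value where required (e.g. shift table".

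Two further rules in the same section matter:
- **Retests:** "In the case of a retest (same visit number assigned), the latest available measurement for that visit will be used for by-visit summaries".
- **Early termination:** values are mapped to the next planned visit. If that visit is more than 14 days away, they go only to MAPVS, MAPLV and the listings.

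The laboratory shifts are specified in SAP 18.2 as "Shift from baseline by treatment and visit of subject with laboratory values below, within, and above the normal range", with a gender version: "Shift from baseline by visit, treatment and by gender of subject for selected serum chemistry parameters". Appendix 4 lists three shift tables. Table 14.3.4.1.2 is "Serum Chemistry: Shift from Baseline by Scheduled Timepoint and Treatment - Injectable Safety Population", Table 14.3.4.2.2 is "Hematology: Shift from Baseline by Scheduled Timepoint and Treatment", and Table 14.3.4.3.2 gives urinalysis in the same form.

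Protocol 14.3.5.2 says: "Shifts from baseline will be produced by treatment to show the percentage of subjects with laboratory test values" below, within and above normal. It does not mention visits for this output.

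**The concern.** SAP 7.3 names the shift table as a place where unscheduled values can count through a worst-case value. Every planned laboratory shift is by visit or scheduled timepoint, which is the kind of summary from which 7.3 excludes them. A programmer following 18.2 and Appendix 4 has no row in which to put them.

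Unscheduled samples are often drawn because something needs checking. The remaining table of laboratory values that takes them is the MAPLV count, whose limits lie well outside the normal range or do not exist for some tests. In a study whose primary endpoints are safety, an out-of-range result in that gap would be visible only to someone reading the listings. No shift table would give the share of subjects at each dose who ever left the normal range.

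**Working it through.** No figure in the plan has to be reproduced. The check sets the sections side by side and traces individual results through the planned outputs.

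**1. Where a worst-case shift could appear.** Both shift bullets in SAP 18.2 are by visit. All three shift table titles in Appendix 4 are by scheduled timepoint. The SAP text defines no worst-case or overall laboratory row. By contrast, SAP 18.3 gives the ECG categories an overall injection-period summary that takes in unscheduled visits.

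**2. Which tests MAPLV covers.** I compared the test list in Protocol Appendix II with the limits in SAP Appendix 3. ALT and AST count from 3 x ULN upwards. Bicarbonate, magnesium, direct bilirubin, indirect bilirubin and all urinalysis tests have no limit.

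**3. Tracing example results** (values chosen for illustration, assumed not clinically significant):

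| Result | Shift table | MAPLV (14.3.4.4) | Listing |
|---|---|---|---|
| Unscheduled ALT at 2 x ULN | Excluded by 7.3 | Not counted, 2 < 3 | Yes, flagged |
| Unscheduled magnesium out of range | Excluded by 7.3 | No limit exists | Yes, flagged |
| ALT at 2 x ULN, early termination on Day 40 | Excluded, 61 − 40 = 21 > 14 | Not counted, 2 < 3 | Yes, flagged |
| Day 15 ALT at 2 x ULN, same-visit retest normal | Retest shown; first value replaced | Not counted, 2 < 3 | Both values |

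**4. When early-termination values fall out.** Post-injection chemistry is scheduled on Days 8, 15, 22, 29, 33 and 61 (protocol Table 2, footnote d). From Day 1 onwards the gaps are 7, 7, 7, 7, 4 and 28 days, so only the last exceeds 14. On nominal days, a termination on Day d after Day 33 is unmapped when 61 − d > 14, that is d < 47. The affected window is Days 34 to 46.

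**5. Routes that remain open.** SAP 18 says clinically significant laboratory results will be listed and summarised. Protocol 11.2 has them recorded as adverse events, which are tabulated. Appendix 4 lists no separate table of clinically significant laboratory results, so the adverse event tables are the concrete output.

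**6. Weight of one subject.** With 6 active subjects per cohort, one subject is 1/6 = 16.7% of a dose group. If all five cohorts run, pooled placebo has 5 x 2 = 10 subjects and one is 10%. The documents give no rate of unscheduled abnormal results, so the expected number affected cannot be calculated.

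**The case against.** The other side has five fair points.

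- **Clinically significant results are not lost.** A reader might infer that unscheduled abnormal values short of the MAPLV limits enter no summary at all. The documents do not support that: values judged clinically significant reach the adverse event tables. The gap is confined to results not so judged. This limit stands, though the judgement is made case by case and does not replace a systematic count.
- **The 7.3 wording is conditional.** It speaks of use where required and gives the shift table as an example, so it is not a firm commitment. That is right, but a named example that matches no planned output still needs resolving.
- **The templates are not in the documents.** SAP 8 says they set table format and content, and titles do not name every panel. SAP 18.2 asks for shifts by gender, yet no laboratory title mentions gender. A worst-case row may exist in the templates. What can be shown is only that the SAP text and table titles do not define one.
- **The protocol does not ask for it outright.** A reader might take shifts by treatment to mean one worst-case shift per subject. The same section does say at each visit for the descriptive statistics, which gives some contrast. A table by treatment and visit is nevertheless still by treatment, so no breach of the protocol is shown.
- **The consequence is small.** Out-of-range values are flagged in the listings, safety groups are not tested against each other, and dose escalation rests on the Safety Review Team's own data review. This stands and sets the size of the point.

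It would also be tempting to size the issue by compounding an assumed abnormality rate over the six chemistry visits. That would describe scheduled data, and would need both a rate and independence between visits that the documents do not give. It does not measure this gap.

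**Conclusion.** The mismatch is real and narrow. As the SAP text and table titles stand, the affected results are unscheduled out-of-range values that lie below a MAPLV limit or have none, and that are not judged clinically significant. They appear only in flagged listings. Unmapped early-termination values in the same range follow them, and an abnormal first result is replaced in the by-visit tables by a later same-visit retest.

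This rests on two assumptions: that the templates contain no worst-case row, and that a shift by scheduled timepoint counts as a by-visit summary under 7.3. The effect on the report is modest, because the analysis is descriptive and the values remain in the listings. It is still worth correcting, because safety is primary, one subject is a sixth of a dose group, and the remedy uses data already collected.

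**What to change.** Add a worst post-baseline row, by treatment, to Tables 14.3.4.1.2, 14.3.4.2.2 and 14.3.4.3.2:

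- For quantitative tests, show each subject's lowest and highest post-injection category against the baseline category.
- For qualitative urinalysis items, where lowest and highest have no meaning, show the worst normal/abnormal category.
- Use all scheduled, unscheduled, retest and unmapped early-termination values after the injection.

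Amend the shift bullet in SAP 18.2 to read: by treatment and visit, and worst post-baseline overall. This gives the example in 7.3 a destination and follows what 18.3 already does for ECG categories.

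Deleting the shift-table example from 7.3 would also remove the inconsistency, but would leave the affected results in listings only.

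The cost is one extra panel in three tables and no new data. Abnormal percentages in the new row would look slightly less favourable than those by visit.

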## 7.4. WINDOWING CONVENTIONS

No visit windowing will be performed for this study.

Refer to appendix 1 for the visit convention for this study.

## 7.5. STATISTICAL TESTS

90% CIs will be used for the PK analysis.

---

Document:

Author:

Version Number:  
Version Date:

Final Draft  
11APR2019

Template No: CS\_TP\_BS016 Revision 4  
Effective Date: 01Apr2016

Reference: CS\_WI\_BS005

## 7.6. COMMON CALCULATIONS

For quantitative measurements, change from baseline will be calculated as:

- Test Value at Visit X – Baseline Value
- For PK computations, the Percentage Coefficient of Variation (CV%), Geometric Mean (Geo Mean), and Percentage Geometric Coefficient of Variation (GCV% or 'Geometric CV%') will be computed as below:

$$CV\% = 100 \frac{SD}{Mean}$$

$$Geo\ Mean = e^{Mean_{Log}}$$

$$GCV\% = (100) \sqrt{(e^{SD_{Log}^2}) - 1}$$

Where SD is the sample standard deviation, Mean is the sample mean, MeanLog is the sample mean of the log transformed data, and SDLog is the sample standard deviation of the log transformed data. Note that when the data are lognormally distributed, CV% and GCV% are equal.

## 7.7. SOFTWARE VERSION

The PK analysis will be conducted using Phoenix® WinNonlin® Version 8.0, or higher (Certara L.P., Princeton, New Jersey). All other analyses will be conducted using SAS Version 9.4 or higher.

## 7.8. MISSING DATA

Missing PK data will be handled as described in Section 17 of this analysis plan.

## 7.9. EXAMINATION OF SUBGROUPS

Hemoglobin, hematocrit, uric acid, serum prolactin and QTcF will be presented by gender.

---

Document:

Author:

Version Number:  
 Version Date:

Final Draft  
 11APR2019

Template No: CS\_TP\_BS016 Revision 4  
 Effective Date: 01Apr2016

Reference: CS\_WI\_BS005

## 8. OUTPUT PRESENTATIONS

Appendix 1 shows conventions for presentation of data in outputs.

The templates provided with this SAP describe the presentations for this study and therefore the format and content of the summary tables, figures and listings to be provided by IQVIA Biostatistics.

## 9. DISPOSITION AND WITHDRAWALS

All subjects who provide informed consent will be accounted for in this study.

The total number of screened subjects, the number of subjects who are screen failures, and the number of subjects randomized will be presented. The number and percentage of subjects who were randomly assigned to the double-blind injection period and the number of subjects in the Oral Lurasidone tablet period will be summarized. Subjects in the PK population will also be summarized. The number and percentage of subjects who complete and discontinue study will be summarized, along with reasons for study discontinuation. Subject disposition will be displayed by treatment (dose level of Lurasidone injectable suspension and pooled placebo) and overall.

Listing of subject disposition will also be provided.

Additionally, screen failure subjects will be presented in a data listing.

## 10. IMPORTANT PROTOCOL DEVIATIONS

Important Protocol Deviations (IPDs) will be identified and documented based on a review of potential IPDs. IPD's or events include any changes to the procedures that may impact the quality of the data or any circumstances that can alter the evaluation of the PK. The potential IPDs will be identified through programmatic checks of study data, as well as through review of selected data listings. The potential IPDs or events to be reviewed include, but are not limited to, subjects who:

- Did not meet inclusion/exclusion criteria.
- Did not meet continuation criteria.
- Received disallowed concomitant medication that is likely to impact the PK of lurasidone or its metabolites.

---

Document:

Author:

Version Number:  
Version Date:

Final Draft  
11APR2019

Template No: CS\_TP\_BS016 Revision 4  
Effective Date: 01Apr2016

Reference: CS\_WI\_BS005

- Informed consent date obtained after date of first study procedure.
- Incomplete Injection dose administered
- Sample processing errors that lead to inaccurate bioanalytical results
- Incomplete PK profile collected

Additional IPDs may be identified from clinical review of Investigator comments or other data. Individual IPDs will be presented in a data listing.

Summary and listing of the IPD will be presented by treatment using ISAF population.

Additionally, listing of subject eligibility including inclusion and exclusion criteria will be presented in a listing.

## 11. DEMOGRAPHIC AND OTHER BASELINE CHARACTERISTICS

Summary of demographic data and other baseline characteristics will be presented for the ISAF population. OSAF population will be used for the listing.

No statistical testing will be carried out for demographic or other baseline characteristics. Data will be summarized by treatment (dose level of Lurasidone injectable suspension and pooled placebo) and overall using descriptive statistics (number of subjects, mean, standard deviation (SD), median, minimum, and maximum) for continues variables, while categorical variables will be presented by number of subjects and percentage.

Additionally, data listing of demographic baseline characteristics will be presented

The following demographic and other baseline characteristics will be reported for this study:

- Age (years) - calculated relative to date of consent
- Sex
- Race
- Ethnicity
- Weight (kg)

---

Document:

Author:

Version Number:  
Version Date:

Final Draft  
11APR2019

Template No: CS\_TP\_BS016 Revision 4  
Effective Date: 01Apr2016

Reference: CS\_WI\_BS005

- Height (cm) - calculated at screening
- BMI (kg/m^2) – calculated at screening
- Baseline PANSS Total Score

## 11.1. DERIVATIONS

- BMI (kg/ m^2) = weight (kg)/ [height (cm)/100]

## 12. MEDICAL HISTORY

Summary of medical history information will be presented for the ISAF population. OSAF population will be used for the listing.

Medical History will be coded using Medical Dictionary for Regulatory Activities (MedDRA v. 20.1 or higher).

- o Medical History conditions are defined as those conditions which stop prior to or at Screening.
- o Presented by SOC and PT.

The number and percentage of subject's medical history in each SOC and each PT will be summarized by treatment (dose level of Lurasidone injectable suspension and pooled placebo) and overall.

Data listing of medical history will also be provided.

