9.5.2. Concomitant Nonpsychotropic Medications

Non-psychotropic medications used to treat mild, chronic medical conditions may be used during Screening and after assignment of a subject number, if the dose and regimen have been stable (\pm 25%) for at least 30 days prior to Screening. The concomitant medication dose may change as needed (or be discontinued) after a subject number is assigned. In addition, use of nonprescription pain medications are allowed during all phases of the study provided these medications do not have a propensity for psychotropic effects and do not interfere with the evaluation of study medication. Medications for short-term treatment of a medical condition (no more than 10 days) are allowed with consultation with the Medical Monitor provided that the medications are not drugs that prolong the QT/QTc interval or CYP3A4 inhibitors or inducers (see Section 22, Appendix IV and Section 23, Appendix V, respectively).

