14.3.4. Demographic and Baseline Characteristics

The number and percentage of subjects in each racial group will be summarized. Age, height, weight, and BMI may be summarized using descriptive statistics (number of subjects, mean, standard deviation, median, minimum, and maximum).

The medical history of subjects will be coded by System Organ Class (SOC) and Preferred Term (PT) using Medical Dictionary for Regulatory Activities (MedDRA v. 20.1 or higher). The number and percentage of subjects with abnormal findings in each SOC and each PT will be summarized

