14.3.5.6. Physical Examination

Findings from the physical examinations will be presented as follows: pre-existing clinically significant conditions recorded as medical history will be summarized, and new clinically significant conditions recorded as an AE will also be summarized.

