### 18.5. PHYSICAL EXAMINATION

The clinically significant abnormalities or changes which are noted in the physical exams are recorded as part of medical history (if noted during screening) and as adverse events at other timepoints. Their summaries/listings are thus included in the medical history and adverse events outputs.

A listing displaying whether a physical examination was performed for each subject and the date of the physical examination. OSAF population will be used.

---

Document:

Author:

Version Number:  
Version Date:

Final Draft  
11APR2019

Template No: CS\_TP\_BS016 Revision 4  
Effective Date: 01Apr2016

Reference: CS\_WI\_BS005

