## APPENDIX 4. LIST OF TABLES, FIGURES, AND LISTINGS

Number	Title
Table 14.1.1	Subject Disposition by Treatment - All Subjects
Table 14.1.2	Important Protocol Deviation (IPD) by Treatment - Injectable Safety Population
Table 14.1.3	Demographics and Baseline Characteristics by Treatment - Injectable Safety Population
Table 14.1.4.1	Medical History by Treatment - Injectable Safety Population
Table 14.1.4.2	Psychiatric History by Treatment - Injectable Safety Population
Table 14.1.5.1	Prior Medications by Treatment - Safety Population
Table 14.1.5.2	Concomitant Medications by Treatment - Safety Population
Table 14.2.1.1	Lurasidone Serum Concentrations (ng/mL) by Scheduled Timepoint and Dose Pharmacokinetic Population
Table 14.2.1.2	Metabolite Serum Concentrations (ng/mL) by Scheduled Time and Dose - Pharmacokinetic Population
Table 14.2.2.1	Lurasidone Serum Pharmacokinetic Parameters by Dose and Gender Following Lurasidone Injection - Pharmacokinetic Population
Table 14.2.2.2	Metabolite Serum Pharmacokinetic Parameters by Dose and Gender Following Lurasidone Injection - Pharmacokinetic Population
Table 14.2.3.1	Dose Proportionality Assessment - Lurasidone - Pharmacokinetic Population
Table 14.2.3.2	Dose Proportionality Assessment - Lurasidone Metabolites - Pharmacokinetic Population
Table 14.2.4.1	Lurasidone Urine Pharmacokinetic Parameters by Dose and Gender Following Lurasidone Injection - Pharmacokinetic Population
Table 14.2.4.2	Metabolite Urine Pharmacokinetic Parameters by Dose and Gender - Pharmacokinetic Population
Table 14.2.5	Positive and Negative Syndrome Scale (PANSS) Total Score: Actual and Change from Baseline by Scheduled Timepoint and Treatment - Pharmacodynamic Population
Table 14.3.1.1	Overall Summary of Adverse Events - Injectable Safety Population
Table 14.3.1.2	All Adverse Events by Treatment - Safety Population

---

Document:

Author:

Version Number:  
 Version Date:

Final Draft  
 11APR2019

Template No: CS\_TP\_BS016 Revision 4  
 Effective Date: 01Apr2016

Reference: CS\_WI\_BS005

Statistical Analysis Plan

PROTOCOL D1052024  
 Page 62 of 66

Number	Title
Table 14.3.1.3	All Adverse Events by Severity and Treatment - Safety Population
Table 14.3.1.4	All Adverse Events by Relationship to Treatment - Safety Population
Table 14.3.1.5	Duration of All Injection Site Reaction Related AEs in Days by Treatment - Injectable Safety Population
Table 14.3.2.1	All Serious Adverse Events by Treatment - Safety Population

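### SAP 12 counts as medical history only conditions that ended by Screening, so non-psychiatric conditions still ongoing at entry fall outside Table 14.1.4.1 and no other planned table reports them

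*SAP*

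**What the plan says.** SAP 12 gives the working definition: "Medical History conditions are defined as those conditions which stop prior to or at Screening". It then plans the summary: "The number and percentage of subject's medical history in each SOC and each PT will be summarized by treatment" and overall. SAP Appendix 4 lists this as Table 14.1.4.1, "Medical History by Treatment - Injectable Safety Population". SAP 12 has no companion category for conditions that have not stopped.

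Three other places bear on the same table:

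- Protocol 14.3.4 plans the medical history summary without any stop-date limit: "The number and percentage of subjects with abnormal findings in each SOC and each PT will be" summarized.
- Protocol 14.3.5.6, on physical examination, says that "pre-existing clinically significant conditions recorded as medical history will be summarized".
- SAP 18.5 says that clinically significant examination findings are "recorded as part of medical history (if noted during screening"), and that they therefore appear in the medical history outputs.

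On who may enter, Protocol 9.5.2 says: "Non-psychotropic medications used to treat mild, chronic medical conditions may be used during Screening and after assignment of a subject number", provided dose and regimen have been stable for at least 30 days before Screening. SAP 4.7 reports no change from the analyses or definitions in the protocol.

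**The concern.** A medical history table in a safety study should show what subjects brought with them into the trial, including what they still had on the day of dosing. The SAP 12 rule selects on the stop date and so keeps the conditions that are over. A programmer who follows it would filter out a treated chronic illness and keep one that resolved years earlier.

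The table gives the by-dose view of comorbidity in a study whose primary endpoints are safety (Protocol 14.1), with 6 active subjects planned per cohort. Protocol 11.1.1 counts worsening of a pre-existing condition as an adverse event. A reader judging whether an event at one dose is new, or whether dose groups and pooled placebo differed at entry, would look to this table first. The concomitant medication table could also show treatments whose underlying conditions are absent from the history table.

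**Working it through.** No arithmetic applies: the documents state no figure on this point. The check is to take each kind of condition and see where the plan sends it.

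1. **Non-psychiatric condition that ended before or at Screening.** It meets SAP 12 and goes into Table 14.1.4.1.
2. **Non-psychiatric condition that began before consent and is ongoing at Screening.** It has not stopped, so it fails SAP 12. It is not a pretreatment event, because Protocol 10.2.1 records these from consent onward and Protocol 10.2.3 adds worsening or change. It is not an adverse event unless it worsens after dosing. The baseline list in SAP 11 (age, sex, race, ethnicity, weight, height, BMI, PANSS total) has no comorbidity item. Appendix 4 has no table of ongoing or concurrent conditions. No planned table reports it.
3. **The same condition, ending between Screening and dosing.** The stop date falls after Screening, so the result is the same as in 2.
4. **Clinically significant examination finding noted at Screening and persisting.** SAP 18.5 puts it into the medical history outputs; SAP 12 keeps it out. The SAP gives two answers.
5. **Psychiatric disorder present at entry.** SAP 13 summarizes schizophrenia and the proportion of subjects with other psychiatric disorders present, in Table 14.1.4.2, "Psychiatric History by Treatment - Injectable Safety Population". This is covered, so the gap is confined to non-psychiatric conditions.

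Against the protocol, the direct conflict is with 14.3.5.6: pre-existing conditions recorded as medical history are to be summarized, with no requirement that they have ended. Protocol 14.3.4 is silent on resolved versus ongoing. It gives no support to the restriction but does not contradict it outright. Since SAP 4.7 declares no changed definitions, the restriction is an undeclared departure from 14.3.5.6.

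Cases 2 and 4 are not remote. Protocol 9.5.2 provides for subjects on continuing treatment for mild chronic conditions, and Protocol 7.1 admits subjects up to age 65 and BMI 38 kg/m².

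**The case against.** Several points on the other side have weight.

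- **SAP 18.5 points the other way.** A reader might infer from SAP 12 that every condition present at entry is lost. The documents do not support that: Screening examination findings are in conflict between two SAP sections, and psychiatric disorders have their own table. This stands and limits the point.
- **The table shells are not in the documents.** SAP 8 says the templates set the format and content of the tables. An ongoing flag may exist there. This stands as a limit on certainty about the final table, but a template does not repair a definition that contradicts it.
- **Other data give context.** A reader might infer that laboratory, ECG and vital-sign results become uninterpretable. They do not: SAP 18.2 to 18.4 read them against each subject's own baseline, with laboratory shifts and markedly abnormal criteria. The CRF records the indication for each concomitant medication (Protocol 9.5), and SAP 14 summarizes concomitant medications by dose and pooled placebo. That is an indirect view of treated comorbidity only.
- **A listing is planned.** Listing 16.2.4.2 may show ongoing conditions, and with small groups individual cases will be read from listings. SAP 12 does not say whether the stop-date rule also governs the listing, and a listing does not provide counts and percentages by dose.
- **Eligibility narrows what can be missing.** Protocol 7.2 excludes, among others, renal or hepatic insufficiency, known or suspected carcinoma, epilepsy and significant disease that poses a health concern. What remains is mostly mild, which lowers the stakes without removing the gap.
- **The verb may be a slip, with stop written for start.** That is possible, but it concedes the correction, since the sentence would be programmed as it stands.

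**Conclusion.** The point holds in this form: read literally, SAP 12 leaves non-psychiatric conditions ongoing at Screening out of Table 14.1.4.1, and no other planned table reports them. The rule contradicts SAP 18.5 and Protocol 14.3.5.6, and SAP 4.7 does not declare it.

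The size is modest. What suffers is the by-dose description of baseline comorbidity and the context for reading adverse events. No test, endpoint, analysis population or dose-escalation rule uses the table. The documents give no count of affected subjects, so no proportion of lost comorbidity can be stated.

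The conclusion assumes that SAP 12 is programmed as worded and that the unseen templates do not override it. It should be corrected before programming, because a stated rule yields the wrong table and the correction is small.

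**What to change.** Replace the definition in SAP 12 with one on these lines: medical history comprises any condition that started before Screening or was first noted at Screening, whether resolved or ongoing. Including findings first noted at Screening matters, because a rule based only on onset before consent would miss examination findings of unknown onset, which SAP 18.5 assigns to medical history. New events with onset after consent should stay pretreatment events, as in Protocol 10.2.1; one clause can say so.

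Show resolved and ongoing conditions as separate blocks in Table 14.1.4.1 where the CRF records status or stop date. Protocol 10.1 says medical history is collected but does not describe the fields, so this needs checking; if neither field exists, present one combined block. State that Listing 16.2.4.2 covers both groups. Align SAP 12 with SAP 18.5 and Protocol 14.3.5.6, after which the SAP 4.7 statement needs no exception on this point.

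The cost is a sentence or two in the SAP and, if the status field exists, one grouping variable in the table. History is already taken at Screening, so no new procedure for subjects appears necessary.
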